Research hypothesis: Patients who are seen during a virtual phone visit will report different PRO and patient satisfaction scores compared to patients who are seen during an in-person visit for post-operative follow-up at 6 weeks, 12 weeks, and 6-months.

5) Background

Since the WHO declared the coronavirus disease 2019 (COVID-19) a global pandemic on March 11, 2020, health systems have had to reorganize and change the way healthcare is provided to patients [1]. An emphasis has been placed on social distancing to limit the spread of the severe acute respiratory syndrome coronavirus 2 (SARS-CoV-2). In the past several months, healthcare has rapidly shifted towards telemedicine to limit the COVID-19 spread. Telemedicine is defined as healthcare where clinicians utilize technology and telecommunications to treat and diagnose patients [2]. Benefits of telemedicine has been found to include decrease healthcare costs, decrease overall appointment times, and similar patient satisfaction [3-4]. During the age of COVID-19, telemedicine has played a vital role in allowing the conservation of resources like personal protective equipment (PPE), decrease in risk of clinician exposure to COVID-19, and maintain social distancing.

Telemedicine has been researched in various medical specialties and have been associated with good outcomes and patient satisfaction scores [5]. Based on the literature, the use of telemedicine in orthopedics has not been extensively studied. There are studies on virtual fracture clinics which have grown in use in the United Kingdom and Ireland, however, they do not utilize a live assessment model [6-8]. One study looks at patient satisfaction of those seen at a regional medical center in rural Norway through telemedicine [9]. Also, there are studies exploring the use of telemedicine to provide follow-up care after

Patient reported outcomes from patients seen in virtual phone visits compared to in-person physical visits for post-operative follow-up at a sports medicine clinic: a prospective randomized controlled trial

total hip and knee arthroplasty [10-13] and the role of telemedicine by physical therapists as a viable option for virtual rehabilitation [14]

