Researchers want to allow patients to have enough time to read the information sheet and consider participation in this study.

In-person consent will be done at any in-person visit including the pre-operative appointment, day of surgery, and at the routine 2-week postop visit.

How: The Participant will be recruited in-person.

Source of the Participants: Patients that present to the Harbor-UCLA Medical Center sports medicine clinic that have scheduled operative intervention.

Methods to identify potential Participants: When patients of the sports medicine clinic have planned operative intervention, study team member will go through the patient charts to see if patient meets criteria and then discuss and consent the Participant in-person.

Materials to recruit Participants: Patients who meet criteria will be given the information study sheet to review on their own.

Patient reported outcomes from patients seen in virtual phone visits compared to in-person physical visits for post-operative follow-up at a sports medicine clinic: a prospective randomized controlled trial

There are no payments to any of the Participants.

b) Inclusion and Exclusion Criteria

Inclusion criteria:

Participants are at least 18 years of age. Participants who are seen at Harbor-UCLA Medical Center sports medicine clinic. Participants have agreed to have operative intervention. Participants must own a phone with reliable calling capabilities. The Participants must have access to reliable internet to fill out the online survey. The Participants must be able to provide consent. Participants may include pregnant patients. Participants who start out in the virtual phone pathway, and the clinician deems person to require an in-person appointment at the 2-week follow-up visit can be moved to the in-person pathway.

Exclusion criteria:

Patients that are under the age of 18, any cognitive impaired adult, and any adult unable to provide consent.

c) Local Number of Participants

For a statistical significance of 0.05, Power of 80%, and assuming a medium effect size of 0.8, 26 patients are required per group for a total of 52 Participants.

The number of Participants need to complete the research procedure are 52.

Locally we will attempt to recruit at least 104 Participants. This will allow room in case of patients are removed or fall from the study.

d) Study-Wide Number of Participants

This is not a multicenter study.

e) Study Timelines

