The study will be ongoing until the appropriate number of Participants are recruited from this site.

The duration of an individual Participant's participation in the study will be from initial visit where consent is asked until completion and submission of the surveys at their 6-month post-operative appointment.

The duration anticipated to enroll all study Participants will be 6 months.

The estimated date for the investigators to complete this study (complete primary analyses) is December 2023.

f) Study Endpoints

Primary study endpoints: Participant reported outcome scores through PROMIS Global.

Patient reported outcomes from patients seen in virtual phone visits compared to in-person physical visits for post-operative follow-up at a sports medicine clinic: a prospective randomized controlled trial

Secondary study endpoints: Patient survey scores for knee injuries via KOOS, and shoulder and elbow injuries via QuickDash. Patient appointment satisfaction scores will be surveyed.

g) Procedures Involved in the Human Research

There are no procedures performed.

The mentioned above surveys will be attached to this document.

Study Design:

In this prospective study, we will enroll patients undergoing operative intervention at a Sports Medicine clinic.

The patient will arrive at the 2 week post-operative appointment to sign the consent form in the presence of study team member and a witness in order to be eligible to participate in the study.

After consent is obtained, the Participant will be randomized to either in-person follow up or virtual phone follow up to take place after the 2-week post-op visit. The virtual visits will occur using the same platforms that they are currently taking place in accordance and required by LA County DHS/HUMC.

The randomization process will utilize block randomization and be conducted by an online program called <http://www.randomization.com>. (Wichmann and Hill, 1982, as modified by McLeod, 1985). The Participant will be assigned a number based on the order the Participant is enrolled in the study and that number will be randomly assigned to a follow-up group based on that number.

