The first page of the survey asks for the Participant's name, date of birth, and preferred language (English or Spanish), how comfortable filling out the form, who is completing the form, which joints, amount of pain, and amount of back pain. The second page of the survey will be a joint specific survey and will depend on the joint selected on the first page and the language chosen. It can be the KOOS, QuickDash Outcome Measure, or PROMIS Global. There is a separate patient satisfaction survey that the patient will complete.

Participants will have appointments with the surgeon for suture removal (10 to 14 days after surgery), and evaluation at 6 weeks, 12 weeks, and 6 months after surgery per usual practice.

The source records that will be used to collect data about the Participants are the surveys, and type of surgery, and results of follow up visits. The data collected will be asked on the surveys which include demographic information- Participants' injury region, age, gender, and time since operative intervention.

Study coordinator will check the upcoming Participant schedule and ensure the correct appointment is scheduled.

h) Data and Specimen Banking

None. No data or specimen banking will be done.

i) Data Management/Statistical Analysis

Statistical analysis will be conducted to compare the total scores of each survey results from participants in the in-person group with participants in the virtual phone group. Each Participant outcomes scores will be averaged with standard deviation calculated.

Participant outcomes scores from each appointment time frame (6-week, 12 week, and 6 months) will be compared across the in-patient group and virtual phone group using Student t-test. Statistical significance will be based on an α level of 0.05.

To determine if there is a difference among the Participants' preference for an in-person visit or telemedicine visit, we will conduct a chi-squared test comparing the percentage of Participant responses from the in-patient group with responses from virtual phone group.

Within each category, to determine if Participant's satisfaction changed as time progressed, we will conduct an Analysis of Variance. This will help us determine

Patient reported outcomes from patients seen in virtual phone visits compared to in-person physical visits for post-operative follow-up at a sports medicine clinic: a prospective randomized controlled trial

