if Participants who experience virtual phone visits start to have changing satisfaction the longer time has elapsed since initial operative intervention.

The PROMIS Global is used to calculate the required sample size as it is the largest range of the outcome measures resulting in the most conservative estimates.

For a statistical significance of 0.05, Power of 80%, and assuming a large effect size of 0.8, 26 Participants are required per group for a total of 52 Participants.

At the end, study data will be exported into excel sheets. All the data collected will be on an excel spreadsheet for purposes of the study. Individual surveys will not be downloaded. At that time, all identifiers will be removed and a de-identified data set is maintained and analyzed. At this time, the study team will not be able to identify which data belongs to which participant. Once this occurs, a subject will not be able to request removal of their data. This spreadsheet will be stored on the secure One Drive Microsoft account which uses double authentication and is provided to all DHS employees. Data originating from the surveys will also be kept in a password-protected location on the Harbor-UCLA One Drive Microsoft account. Data will be stored for 3 years after study completion. Access to the data will be given only to those registered with the study.

Signed consent documents any other paper records are kept in a locked cabinet in a locked office with limited access. The data will be stored for 3 years after completion of the research project.

The only individuals with access to the information will be members of the study team.

j) Confidentiality

A list of Participants participating in the study will include the Participant's name, element of dates, which experiment group the Participant is a part of, MRN, and phone number and email, and study ID number. No health information is recorded with this list. This list is kept on the Harbor-UCLA One Drive Microsoft account and available to the research team. All health data required will be recorded in REDCap hosted by Lundquist and the data will include direct identifiers such as name.

k) Provisions to Monitor the Data to Ensure the Safety of Participants

This research does not result in more than minimal risk to the Participants.

l) Withdrawal of Participants

Participants can withdraw from the study at any time.

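### The range of PROMIS Global plays no part in the sample size, so calling it the most conservative basis is wrong; joint-specific KOOS and QuickDASH comparisons would need more than 52 completers at the same effect size

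*Combined protocol and SAP*

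**What the plan says.** Section 9(f) names PROMIS Global as the only primary endpoint. The secondary endpoints include "Patient survey scores for knee injuries via KOOS, and shoulder and elbow injuries via QuickDash", together with appointment satisfaction.

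Section 9(i) compares scores between the two groups at each visit by Student t-test; "Statistical significance will be based on an α level of 0.05". It says PROMIS Global was chosen for the sample size because "it is the largest range of the outcome measures resulting in the most conservative estimates". The calculation is then given as "Power of 80%, and assuming a large effect size of 0.8, 26 Participants are required per group for a total of 52 Participants". No standard deviation, score range or difference in points is stated for any instrument.

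Section 9(c) gives the same calculation "assuming a medium effect size of 0.8"; section 9(i) gives it "assuming a large effect size of 0.8". Section 9(c) requires 52 participants to complete and aims to recruit at least 104, to allow for losses.

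Section 9(g) describes the survey content in two ways. Its numbered list gives KOOS, QuickDASH and PROMIS Global as surveys for the participant, with no joint condition, although it describes KOOS as knee-specific. Its later description of the online form says "The second page of the survey will be a joint specific survey and will depend on the joint selected", and then names PROMIS Global as one of the three possible forms for that page.

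**The concern.** Calling the chosen basis the most conservative among the outcome measures is a claim about the design: that a calculation on any other measure would not have asked for more patients. The reason offered, range, is not an input to the calculation. For measures given to only some of the patients, the claimed property also runs the wrong way, because a test on part of the sample has less power than a test on all of it.

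Two things are at stake. A null KOOS or QuickDASH result could be read as evidence of no difference when the comparison had little chance of detecting even 0.8 SD. And if the form description in section 9(g) is taken literally, the primary endpoint is itself collected from only some participants, and the stated 80% power does not hold for it.

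**Working it through.** **Inputs.** Alpha 0.05, power 80%, standardised effect d = 0.8, 26 per group, 52 completers, t-test (sections 9(c) and 9(i)). The number of sides is not stated. Two-sided is assumed, because section 4 hypothesises that virtual-visit patients "will report different PRO and patient satisfaction scores compared to patients who are seen during an in-person visit", and because only the two-sided calculation returns the stated number. The share of patients with each joint is not in the documents; every share below is an assumption.

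**Step 1: reproduce the plan's figure.** For n per arm, power is the probability that a noncentral t variable with 2n − 2 degrees of freedom and noncentrality d × √(n/2) falls beyond the two-sided 5% critical value.
- n = 26: noncentrality 0.8 × √13 = 2.88, 50 degrees of freedom, power 80.7%.
- n = 25: power 79.1%.
- The exact solution is 25.5, rounded up to 26 per group, 52 in total. The stated figure reproduces.
- The normal approximation gives 25 per group two-sided and 20 one-sided; the latter does not match.

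**Step 2: does range matter?** d is the difference divided by the SD. Multiplying both by 0.5, 1, 2 or 4 leaves d at 0.8 and the solution at 25.5 each time. The result is the same for an instrument of any range. Range could matter only indirectly, if one difference in points were assumed for every instrument and a wider range brought a larger SD. The plan states no such difference and no SD.

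**Step 3: joint-specific instruments with 52 completers.** Take n per arm = 52 × share / 2, with d = 0.8. This splits each joint group evenly between arms, which is the most favourable split; section 9(g) describes block randomisation and mentions no stratification by joint. Fractional n per arm are expected values.

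| Share completing the instrument (assumed) | n per arm | Power at d = 0.8 |
|---|---|---|
| 25% | 6.5 | 26% |
| 33% | 8.7 | 35% |
| 50% | 13 | 50% |
| 67% | 17.3 | 63% |
| 70% | 18.2 | 65% |
| 90% | 23.4 | 76% |
| 100% | 26 | 81% |

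One result needs no assumed mix. If nobody completes both joint forms, the two shares add to at most 100%, so the smaller is at most 50%. That means at most 13 per arm and at most about 50% power. The effect detectable with 80% power is about 1.15 SD at 13 per arm and about 1.44 SD at 8.7 per arm.

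**Step 4: total needed for 26 per arm within a joint group.** The total is 52 / share: 208 at 25%, 156 at 33%, 104 at 50%, 78 at 67%, 70 at 75%. Every share below 100% needs more than 52, so PROMIS Global completed by everyone is the least demanding of the three at a common d.

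**Step 5: PROMIS Global under the literal form description.** If it is one of three joint-dependent alternatives, its n per arm is also 26 × its share, and the table in Step 3 applies to the primary endpoint too.

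**The case against.** The strongest reply is that nothing is wrong with the number. PROMIS Global is the sole primary endpoint, sizing on the primary endpoint is normal practice, and 26 per group reproduces. The plan makes no explicit power claim for KOOS or QuickDASH. All of that stands.

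A reader might infer that the plan promises 52 is enough for every outcome measure. It does not say so; that is at most an implication of the word conservative.

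A reader might also infer that both joint-specific comparisons fall far below 80% power. The documents do not support that either. A joint making up 90% of patients would have 76% power, and if all 104 recruits completed, an instrument with a 50% share would reach 81%. Against the latter, 104 is an allowance for loss and 52 is the number required to complete. Even the limit on the smaller group assumes that the groups do not overlap, and the form asks which joints are affected, so some overlap is possible.

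Finally, the numbered list in section 9(g) can be read as giving every instrument to everyone, in which case subset size would not arise. The endpoint definitions in section 9(f) and the joint-dependent page point the other way. The conflict has to be resolved in the protocol, and on no reading does range enter the calculation.

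On the label, a reader might infer from *medium* in section 9(c) that a smaller effect was intended. Both sections use 0.8 and reach 26 per group, so this is an inconsistent adjective and not a second calculation.

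**Conclusion.** The rationale in section 9(i) is wrong and should go. Range has no role in a calculation on d = 0.8, and under the joint-specific scheme sizing on PROMIS Global is not conservative relative to KOOS or QuickDASH. This does not make 52 wrong for the primary endpoint: 26 per group gives 80.7% power for 0.8 SD, two-sided, on condition that every participant completes PROMIS Global. The documents are inconsistent on that condition, and this is the most consequential part of the point.

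For the secondary endpoints, with 52 completers, non-overlapping joint groups and an even split between arms, the smaller group has at most about 50% power. The larger group's power cannot be stated without a joint mix; 65% and 76% at shares of 70% and 90% are illustrations. Low power in secondary subsets is a limitation to declare, not an error in the sample size.

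**What to change.** - Delete the sentence that rests the choice of PROMIS Global on its range and calls it conservative. If a rationale is wanted, say that it is the primary endpoint, or give a PROMIS Global difference and SD.
- State that 26 per group gives 80% power for a 0.8 SD difference in PROMIS Global only.
- Reconcile the survey list and the form description in section 9(g) so that PROMIS Global is collected from every participant and it is clear who completes KOOS and QuickDASH.
- Describe KOOS and QuickDASH as secondary subset comparisons with limited power, reported as estimates with confidence intervals. Give a power figure only alongside a stated expected joint mix.
- Use one label for the 0.8 effect in sections 9(c) and 9(i): *large*, as section 9(i) already has it.

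The cost is wording and a less favourable description of the secondary endpoints. No additional patients are needed. If PROMIS Global is not at present given to everyone, adding it to every participant's form is a small change to the survey.

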However, there are few studies looking at PROs in patients receiving orthopaedic care through telemedicine. PROs are an important marker of quality distinct from patient satisfaction because PROs are standardized metrics of healthcare delivery. One study looked at the accuracy of physical exams and patient satisfaction from post-operative follow up for arthroscopic knee procedures [15]. A study by Sathiyakumar et al looked at patient satisfaction scores during follow up from operative and non-operative management of orthopedic trauma injuries and found similar satisfaction scores between both groups [4]. Two studies collected both PROs and patient satisfaction scores of patients who attended telemedicine orthopaedic appointments. In Sharareh et al's study, telemedicine visits are used to supplement physical follow up visits for patients that receive total joint arthroplasty [13]. In the other study by Grandizio et al, patients are seen for post-operative follow-up for upper extremity orthopaedic injuries and had similar patient satisfaction scores, however PROs are not compared [16].

Before the COVID-19 pandemic, the standard of care was that after surgery, patients are seen for in-person follow up. Due to the COVID-19 pandemic, the standard of care has changed. Currently, at Harbor-UCLA Medical Center, many clinics and providers have started utilizing virtual phone appointments to see patients to allow social distancing amidst the COVID-19 pandemic. The providers have been determining if a patient requires an in-person visit or if a virtual phone visit would be appropriate. Virtual phone visits have been used for post-operative appointments, to complete pre-surgical history and physicals, and assessment of chronic medical conditions. With this study, we are creating controlled circumstances to determine if patients who receive virtual phone visits are satisfied with their care and report similar outcomes.

We would like to analyze PROs and patient satisfaction scores of patients that attend virtual phone visits for sports medicine injuries and compare them to scores from in-person physical visits. We will collect PROs and patient satisfaction scores from patients who attend appointments at their 6-week, 12-weeks and 6-month post-operative appointments.

6) Setting of the Human Research

Harbor-UCLA Department of Orthopaedic Surgery Sports Medicine Clinic

7) Resources Available to Conduct the Human Research

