The Participant will be notified at the 2-week post-op or after if they will receive in-person follow up or virtual phone follow-up. If the Participant in the virtual phone group feel they need an in-person visit, the Participant will be free to make an in-person follow-up. After each follow up visit (6-week, 12-week, and 6-month), the Participant will be asked to fill out 30-minute surveys.

The surveys the Participant will be asked to fill out are the following:

1. KOOS- a knee specific survey
2. Quick Dash Outcome Measure
3. PROMIS Global
4. General Health Questionnaires (2)
5. Patient Satisfaction Survey -We will have the patient complete this also after every visit to see if their preferences change over time as their recovery changes.

If a Participant attends an in-person post-operative follow up visit, then the study team member will check to see if the participant is on the in-person list. If the participant is on the list, then he or she will be given a tablet to fill out the online survey after the appointment. The tablet will be set up so a link to the surveys can be accessed and participants can fill out the surveys. The surveys are on REDCaps (<https://research.lundquist.org/redcap/surveys/?s=NK3YH4NWL3>). Patients will be able to fill out the survey at home. For Participants that attend a virtual appointment, an online

Patient reported outcomes from patients seen in virtual phone visits compared to in-person physical visits for post-operative follow-up at a sports medicine clinic: a prospective randomized controlled trial

link to the survey on REDCap will be sent to the Participant's email. Members of the study team can also call the participant to conduct the survey over the phone. The emails will be made secure by having them sent out from an official DHS email that uses Microsoft outlook and requires double verification to logon. The content of the email message is included in the IRB submission as a separate document.

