The procedure for orderly termination is that the Participant will notify any staff member including nurses or providers. The study coordinator will be notified and the Participant's name, MRN, and email will be removed from the data list.

The Participant's survey responses will be linked to Patient identifiers so it will be possible to eliminate the Participant's responses.

Patient reported outcomes from patients seen in virtual phone visits compared to in-person physical visits for post-operative follow-up at a sports medicine clinic: a prospective randomized controlled trial

10) Risks to Participants

Participants may feel inconvenienced having to stay 30 minutes longer to complete the survey on the tablets if you are attending an in-person visit.

Participants may also experience inconvenience or frustration if the survey system freezes and does not operate appropriately. You may also feel bored or tired.

Risk Mitigation

The exclusion criteria exclude any minors, prisoners, and adults who cannot give consent, from participating in the study.

Participants will be given the opportunity to pick a time convenient for them to answer the questionnaires after the virtual phone visit. Participants part of the in-person visit will answer surveys after the visit. Participants are encouraged to answer all questions. If they skip any questions or the survey is not answered completely, their survey may be removed. Participants may stop at any time. They may skip any questions they do not wish to answer, and they may stop at any time. Participants may withdraw from the study at any time. To decrease risk mitigation, the data will be kept on REDCap hosted by Lundquist. Only members of the research team will have access to the data information.

11) Potential Benefits to Participants

We cannot promise any benefits to Participants or others from taking part in this research. We cannot promise any benefits to others from taking part in this research.

The study poses no more than minimal risk with the main risk a breach of confidentiality and the study involves ensuring patient reported outcome surveys completed consistently (which is currently not done in the current clinical setting) and scoring calculated and recorded in the medical record

12) Provisions to Protect the Privacy Interests of Participants

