All participation and questionnaires in this study are optional. It is made clear to the Participants that their participation is voluntary. If Participants would like additional appointments, they are free to contact their provider to schedule another one.

Participants that are in the virtual phone group are free to contact their provider to schedule an in-person visit if they choose to or if their provider would like to see them for an in-person visit. Participating in the study, completing the surveys will not impact the quality of care provided to the participant.

13) Compensation for Research-Related Injury

This research does not involve more than minimal risk.

14) Economic Burden to Participants

There is no economic burden to Participants. There is the burden of time to participate and fill out the survey.

Patient reported outcomes from patients seen in virtual phone visits compared to in-person physical visits for post-operative follow-up at a sports medicine clinic: a prospective randomized controlled trial

15) Consent Process

The Participants will be identified as patients presenting at the Harbor-UCLA Orthopaedics Sports medicine clinic who agree to operative intervention. Patients will receive a study consent form to review on their own. The study team member will go through the patient charts to determine patients that meet the inclusion criteria and then provide the patient with the study consent form. At the pre-operative visit for surgical planning and signing of the surgical consents, all patients will be given a study consent form and asked to participate in the study. The study will be explained to the patient, questions will be encouraged and answered, and the patient will be asked to sign the consent if they wish to participate in the study.

A member of the research team will make it clear that the patient can come in for an in-person visit if they wish and at any time for their post-operative care. The patient can also choose to spend more time to considering participating in the study.

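### Neither phone-to-in-person conversions nor post-operative events are defined or compared by randomised arm, so similar survey scores would not show how many phone patients had to be seen in person or had a clinical event

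*Combined protocol and SAP*

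**What the plan says.** **Current care and allocation.** Section 5 describes present practice at the centre: "The providers have been determining if a patient requires an in-person visit or if a virtual phone visit would be appropriate". In the trial, allocation decides the visit type after the 2-week visit (section 9g): "After consent is obtained, the Participant will be randomized to either in-person follow up or virtual phone follow up".

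**Routes back to an in-person visit.** There are three:
- Section 9b covers participants who start in the phone pathway where "the clinician deems person to require an in-person appointment at the 2-week follow-up visit can be moved to the in-person pathway".
- Section 9g gives the patient the same freedom later: "If the Participant in the virtual phone group feel they need an in-person visit, the Participant will be free to make an in-person follow-up".
- Section 12 adds the provider: phone participants are "free to contact their provider to schedule an in-person visit if they choose to or if their provider would like to see them".

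**Risks and monitoring.** Section 10 begins with "Participants may feel inconvenienced having to stay 30 minutes longer to complete the survey on the tablets" and goes on to frustration with the survey system, boredom and tiredness. Section 11 calls a confidentiality breach the main risk. Section 9k, whose title promises provisions for monitoring safety, consists of one sentence: "This research does not result in more than minimal risk to the Participants".

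**Endpoints and analysis.** Section 9f lists PROMIS Global (primary), then KOOS, QuickDash and appointment satisfaction. Section 9i plans t-tests of survey scores at each visit, a chi-squared test of visit preference, and an analysis of variance of satisfaction over time. Section 9g names the source records as "the surveys, and type of surgery, and results of follow up visits", but no variable or analysis is built on the last of these.

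**The concern.** Visit type is the intervention. The plan itself foresees that some phone patients will be seen in person, because the patient or the provider wants it, yet it never counts them. Nor does it count unscheduled visits, readmissions, reoperations or complications.

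Section 5 says the trial will show whether phone patients are satisfied and report similar outcomes. A reader who is given similar mean scores will want to know two things. How much of the phone arm was actually followed by phone? Did anything clinical happen that a mean score would not identify or date? As written, the report could answer neither.

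Conversion also matters to the survey comparison itself. A phone patient who is seen in person receives part of the other arm's care, which would tend to pull the arms together. The plan does not say in which arm such a patient is analysed.

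**Working it through.** **1. The plan's sample size.** Inputs from sections 9c and 9i: alpha 0.05 (two-sided assumed), power 80%, d = 0.8.
- Normal approximation: n = 2(1.960 + 0.842)² / 0.8² = 15.70 / 0.64 = 24.5, so 25 per arm.
- Two-sample t-test: 25.52, so 26 per arm, with power 80.7% at 26.

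The stated 26 per group (52 in total) reproduces. The recruitment target of at least 104 gives 52 per arm if allocation is 1:1 and nobody is lost.

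**2. What uncounted conversion does to the survey comparison.** The documents give no conversion rate, so a range c is assumed. Suppose that converted patients carry none of the effect and are analysed as randomised. Then effective d = 0.8 × (1 − c).

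| Converted, c | Effective d | Power, 26 per arm | Power, 52 per arm |
|---|---|---|---|
| 0% | 0.80 | 81% | 98% |
| 10% | 0.72 | 72% | 95% |
| 20% | 0.64 | 62% | 90% |
| 30% | 0.56 | 51% | 81% |

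**3. How well a conversion rate could be reported.** Exact 95% intervals for illustrative counts: 5 of 26 (19%) gives 6.6% to 39.4%; 10 of 52 (19%) gives 9.6% to 32.5%. These are wide but informative.

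**4. What the trial could say about events.** With zero events in n phone patients, the one-sided 95% upper limit is 1 − 0.05^(1/n):
- n = 26: 10.9%
- n = 52: 5.6%

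The upper end of the two-sided exact interval, 1 − 0.025^(1/n), is 13.2% and 6.8%.

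For a comparison between arms, take complication rates of 5% and 15%. These are assumed, since the documents give none. The number per arm for 80% power is [1.960√(2 × 0.10 × 0.90) + 0.842√(0.05 × 0.95 + 0.15 × 0.85)]² / 0.10² = (0.832 + 0.352)² / 0.01, or 141 after rounding up. Power is 22% at 26 per arm and 40% at 52. Only descriptive reporting is realistic.

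**5. Survey delivery to a converted patient.** Section 7 gives a tablet to any participant attending in person. Section 9g first checks that the participant is on the in-person list, and sends the email link to those who attend a virtual appointment. Under 9g, a phone-arm patient who comes in has no stated delivery step. The two sections need to be reconciled.

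**The case against.** The strongest reply is about scope. The objectives concern patient-reported outcomes and satisfaction, and the hypothesis is a difference. The protocol claims neither safety nor equivalence, so event endpoints partly extend its aim. That stands, and it is why the request is for descriptive reporting.

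A reader might also draw stronger conclusions that the documents do not support:
- *That randomisation removes provider judgement.* It constrains it. Sections 9b and 12 let the clinician bring a phone patient in, section 15 lets the patient come in at any time, and 9g schedules a surgeon visit for suture removal at 10 to 14 days.
- *That survey inconvenience is the only listed risk.* Section 11 names confidentiality as the main one.
- *That the trial reports nothing but survey means.* Section 9i also tests visit preference and satisfaction over time.
- *That missed or late complications are the main harm of phone visits.* This is an inference. The documents give no complication rate and no evidence of delayed detection, and a severe problem might show in PROMIS, KOOS or QuickDash scores.
- *That uncounted conversions make a null result uninterpretable.* An as-randomised comparison still estimates the effect of phone follow-up with in-person access.

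One objection limits the remedy. In-person patients are examined at each visit, so their complications are more likely to be charted. The same chart search in both arms does not equalise detection, and a raw comparison of complications could wrongly favour phone visits.

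What remains is that the routes back are written into the plan, which makes conversion a foreseeable event, and the plan does not report it.

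**Conclusion.** The point holds as a gap in reporting. The protocol names no risk of the visit type, and 9f and 9i neither define nor compare conversions or post-operative events by arm.

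Under the no-effect assumption for converted patients, 10% to 30% conversion costs roughly 9 to 30 percentage points of power at 26 per arm (81% to 72% or 51%), and 3 to 17 points at 52 per arm (98% to 95% or 81%). The conversion rates are assumed, and the 52-per-arm figures also assume no loss to follow-up. The loss is smaller if converted patients keep part of the effect.

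The documents do not show that phone follow-up is unsafe, and a trial of this size could not show that it is safe: even zero events among 26 or 52 phone patients would leave a one-sided upper limit of 10.9% or 5.6%. The omission is worth correcting because correction is cheap and changes what a finding of similar scores can support.

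**What to change.** **In sections 9f and 9i**, add descriptive reporting by randomised arm, from randomisation to the 6-month visit, as counts with exact 95% confidence intervals:
- (a) Conversions from phone to in-person, including pathway moves at the 2-week visit, with timing and whether the patient or the provider initiated them.
- (b) Unscheduled visits, readmissions, reoperations and charted complications, with date of detection.

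Use the same chart search and time window in both arms, whether or not the survey was returned.

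**Analysis and survey delivery.** State that converted participants stay in their randomised arm for analysis. State also that they receive the survey whether or not they are on the in-person list, and align sections 7 and 9g accordingly.

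**Linkage.** Abstract and link the chart data before identifiers are removed at export (section 9i). The study list in section 9j already holds record number, group and study ID.

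**Interpretation.** State that the trial is not powered for safety. Give more weight to conversions, readmissions and reoperations than to charted complications, which may be under-recorded in patients who are not examined.

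**Cost.** A protocol amendment and one chart abstraction per participant by the existing team, which is work beyond its present eligibility screening. No extra visits or patients are needed. Check that the health-information authorization, which is not in the text available here, covers the abstraction. Events will be few and the intervals wide, and detection bias will remain.
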